10.7. Appendix 7: Abbreviations and Definitions

Term	Definition
ALT	alanine aminotransferase
AST	aspartate aminotransferase
complaint	A complaint is any written, electronic, or oral communication that alleges deficiencies related to the identity, quality, purity, durability, reliability, safety or effectiveness, or performance of a drug or drug delivery system.
compliance	Adherence to all study-related, good clinical practice (GCP), and applicable regulatory requirements.
CRP	clinical research physician: Individual responsible for the medical conduct of the study. Responsibilities of the CRP may be performed by a physician, clinical research scientist, global safety physician or other medical officer.
DMC	data monitoring committee. A data monitoring committee, or data monitoring board (DMB) is a group of independent scientists who are appointed to monitor the safety and scientific integrity of a human research intervention, and to make recommendations to the sponsor regarding the stopping of a study for efficacy, or for harms, or for futility. The composition of the committee is dependent upon the scientific skills and knowledge required for monitoring the particular study.
ECG	Electrocardiogram
enroll	The act of assigning a participant to a treatment. Participants who are enrolled in the study are those who have been assigned to a treatment.
enter	Participants entered into a study are those who sign the informed consent form directly or through their legally acceptable representatives.
GCP	good clinical practice
IB	Investigator's Brochure
ICF	informed consent form
ICH	International Council for Harmonisation
IMP	Investigational Medicinal Product
informed consent	A process by which a participant voluntarily confirms his or her willingness to participate in a particular study, after having been informed of all aspects of the study that are relevant to the participant's decision to participate. Informed consent is documented by means of a written, signed and dated informed consent form.
interim analysis	An interim analysis is an analysis of clinical study data, separated into treatment groups, that is conducted before the final reporting database is created/locked.

investigational product	A pharmaceutical form of an active ingredient or placebo being tested or used as a reference in a clinical trial, including products already on the market when used or assembled (formulated or packaged) in a way different from the authorized form, or marketed products used for an unauthorized indication, or marketed products used to gain further information about the authorized form.
ITT	intention to treat: The principle that asserts that the effect of a treatment policy can be best assessed by evaluating on the basis of the intention to treat a participant (that is, the planned treatment regimen) rather than the actual treatment given. It has the consequence that participant allocated to a treatment group should be followed up, assessed, and analyzed as members of that group irrespective of their compliance to the planned course of treatment.
participant	Equivalent to CDISC term “subject”: an individual who participates in a clinical trial, either as recipient of an investigational medicinal product or as a control
PC	product complaint
PK/PD	pharmacokinetics/pharmacodynamics
PPS	per-protocol set: The set of data generated by the subset of participant who sufficiently complied with the protocol to ensure that these data would be likely to exhibit the effects of treatment, according to the underlying scientific model.
QTc	corrected QT interval
SAE	serious adverse event
SAP	statistical analysis plan
screen	The act of determining if an individual meets minimum requirements to become part of a pool of potential candidates for participation in a clinical study.
TEAE	Treatment-emergent adverse event: An untoward medical occurrence that emerges during a defined treatment period, having been absent pretreatment, or worsens relative to the pretreatment state, and does not necessarily have to have a causal relationship with this treatment.

10.8. Appendix 11: Protocol Amendment History

The Protocol Amendment Summary of Changes Table for the current amendment is located directly before the Table of Contents (TOC).

Amendment a: 04-August-2021

Overall Rationale for the Amendment:

Section # and Name	Description of Change	Brief Rationale
1.1 Synopsis and 4.1.2 Treatment and Assessment Period	Study design amended to move last outpatient visit from Day 27 to Day 28.	To extend the treatment period by 1 day in order to accommodate a longer PK sampling profile to match Stage 1 and Stage 2 PK sampling.
1.3 Schedule of Activities (SoA) – Stages 1 and 2	Study design amended to move last outpatient visit from Day 27 to Day 28.	To extend the treatment period by 1 day in order to accommodate a longer PK sampling profile to match Stage 1 and Stage 2 PK sampling.

Amendment b: 13-August-2021

Overall Rationale for the Amendment:

Section # and Name	Description of Change	Brief Rationale
1.3 Schedule of Activities (SoA) – Stages 1 and 2	
 PK samples - Selpercatinib (plasma) amended to remove 168, 192, 216, and 240 hours postdose on Days 1 and 15. Added PK samples - Selpercatinib (plasma) timepoints in tabular format and deleted the information “Samples will be taken at the following timepoints on Days 1 and 15: predose, and 0.5, 0.75, 1, 1.5, 2, 2.5, 3, 3.5, 4, 6, 8, 12, 24, 36, 48, 72, 96, 120, 144 hours postdose” from footnote of Schedule of Activities (SoA) table for consistent presentation. Added gastric pH (Stage 1 only) timepoints in tabular format and deleted the information “Measurements will be taken at the following timepoints on Days 1 and 15: predose, and 0.5, 1, 1.5, 2, 2.5, 	
 PK samples - Selpercatinib (plasma) timepoints were inadvertently added in previous versions of protocol (Original and amendment a) which have been corrected in current Protocol Amendment (b). Final safety assessments were inadvertently missed in the table.

Section # and Name	Description of Change	Brief Rationale
	
3, and 3.5 hours postdose” from footnote of SoA table for consistent presentation.
 
 Added final safety assessments on Day 28: physical examination, weight, pregnancy test, 12-lead ECG, vital signs, and clinical laboratory tests 	

2. ABBREVIATIONS

Abbreviations pertain to the Statistical Analysis Plan (SAP) only (not the tables, figures and listings [TFLs]).

AE	Adverse event
AUC	Area under the concentration versus time curve
AUC(0-∞)	Area under the concentration versus time curve from time zero to infinity
AUC(0-t _{last})	Area under the concentration versus time curve from time zero to time t, where t is the last time point with a measurable concentration
BE	Bioequivalence
BQL	Below the quantifiable lower limit of the assay
CI	Confidence interval
CL/F	Apparent total body clearance of drug calculated after extra-vascular administration
C _{last}	Last quantifiable drug concentration
C _{max}	Maximum observed drug concentration
CRF	Case Report Form
CRU	Clinical Research Unit
CSR	Clinical Study Report
CV	Coefficient of variation
ECG	Electrocardiogram
GMR	Geometric mean ratio
ICH	International Conference on Harmonisation
MedDRA	Medical Dictionary for Regulatory Activities
NG	Nasal gastric
PD	Pharmacodynamic
PK	Pharmacokinetic
SAE	Serious adverse event
SAP	Statistical Analysis Plan
SD	Standard deviation
t _{1/2}	Half-life associated with the terminal rate constant (λ_z) in non-compartmental analysis
TEAE	Treatment-emergent adverse event

TFLs	Tables, Figures, and Listings
t_{max}	Time of maximum observed drug concentration
V_{ss}/F	Apparent volume of distribution at steady state after extravascular administration
V_z/F	Apparent volume of distribution during the terminal phase after extra-vascular administration
WHO	World Health Organization

3. INTRODUCTION

This SAP has been developed after review of the Clinical Study Protocol (final version dated 19 July 2021), Protocol Amendment (a) (final version dated 04 August 2021), Protocol Amendment (b) (final version dated 13 August 2021), and Protocol Amendment (c) (final version dated 14 October 2021).

This SAP describes the planned analysis of the safety, tolerability, pharmacokinetic (PK) and pharmacodynamic (PD) data from this study. A detailed description of the planned TFLs to be presented in the clinical study report (CSR) is provided in the accompanying TFL shell document.

The intent of this document is to provide guidance for the statistical and PK analyses of data. In general, the analyses are based on information from the protocol, unless they have been modified by agreement with Eli Lilly and Company. A limited amount of information concerning this study (e.g., objectives, study design) is given to help the reader's interpretation. For open-label studies, this SAP must be signed off prior to first participant visit for this study. When the SAP and TFL shells are agreed upon and finalized, they will serve as the template for this study's CSR.

This SAP supersedes the statistical considerations identified in the protocol; where considerations are substantially different, they will be so identified. If additional analyses are required to supplement the planned analyses described in this SAP, they may be performed and will be identified in the CSR. Any substantial deviations from this SAP will be agreed upon with Eli Lilly and Company and identified in the CSR. Any minor deviations from the TFLs may not be documented in the CSR.

This SAP is written with consideration of the recommendations outlined in the International Conference on Harmonisation (ICH) E9 Guideline entitled Guidance for Industry: Statistical Principles for Clinical Trials¹ and the ICH E3 Guideline entitled Guidance for Industry: Structure and Content of Clinical Study Reports².

4. STUDY OBJECTIVES AND ENDPOINTS

Objectives	Endpoints
Primary	
To evaluate the bioequivalence (BE) of a single 160-mg dose of selpercatinib as the tablet formulation (test) compared to the commercial capsule formulation (reference)Maximum observed drug concentration (C_{max}), area under the concentration versus time curve from time zero to infinity ($AUC[0-\infty]$), and area under the concentration versus time curve from time zero to time t, where t is the last time point with a measurable concentration ($AUC[0-t_{last}]$) of selpercatinib
Secondary	
To describe the safety and tolerability of a single 160-mg oral dose of selpercatinibSummary of the number of treatment-emergent adverse events

as the tablet formulation (test) compared to the commercial capsule formulation (reference)	(TEAEs) and serious adverse events (SAEs)
Exploratory 
To determine whether the PK of selpercatinib are altered by initial pH	
C_{max}, $AUC(0-\infty)$, and time of maximum observed drug concentration (t_{max}) of selpercatinib

5. STUDY DESIGN

5.1 Overall Design

Study J2G-MC-JZJZ will be a Phase 1 open-label, randomized, two-period, two-formulation, two-sequence, two-stage adaptive crossover study in adult healthy male and female participants. The new 160 mg tablet will be compared to 2×80 mg commercially available capsules (160 mg is the highest approved dose). [Figure 1](#) below illustrates the study randomization and crossover schema.

Two by Two Crossover Design (Applicable to Stage 1 and Stage 2)

[figure not shown]

Figure 1: J2G-MC-JZJZ Study Schema

Exploratory analysis of pH measurements (done via nasal gastric [NG] tube insertion and aspiration of gastric secretions and testing via pH meter) will be included in Stage 1 to understand the pH dynamics, including the potential of pH effect on absorption. The pH will not be measured in Stage 2 of the study.

Safety assessments, including adverse events (AEs), concomitant medications, medical assessments, clinical laboratory tests, vital signs, and electrocardiograms (ECGs), and blood sampling for PK, will also be performed.

5.1.1 Screening

All participants will be screened within 28 days prior to enrolment.

5.1.2 Treatment and Assessment Period

Stage 1:

Participants will be admitted to the clinical research unit (CRU) on Day -1. On the morning of Day 1, participants will be randomized to receive a single oral dose of 160-mg selpercatinib as the capsule or tablet formulation, and will be dosed according to the randomization sequence following an overnight fast of at least 10 hours. On Day 1, participants will have an NG tube placed in the stomach prior to dosing to assess gastric pH. Participants will remain resident at the CRU until discharge on Day 7.

Participants will attend outpatient visits for the collection of PK blood samples and assessment of vital signs on Days 9 and 11.

Participants will be re-admitted to the CRU on Day 14 and in the morning of Day 15 will receive their second single oral dose of 160-mg selpercatinib as the capsule or tablet formulation, according to the randomization schedule, following an overnight fast of at least 10 hours. On Day 15, participants will have an NG tube placed in the stomach prior to dosing to assess gastric pH. Participants will remain resident at the CRU until discharge on Day 21.

Participants will attend outpatient visits for the collection of PK blood samples and assessment of vital signs on Days 23, 25, and 28.

There will be a washout of at least 14 days between doses of selpercatinib.

Stage 2:

Participants will be admitted to the CRU on Day -1. On the morning of Day 1, participants will be randomized to receive a single oral dose of 160-mg selpercatinib as the capsule or tablet formulation, and will be dosed according to the randomization sequence following an overnight fast of at least 10 hours. Participants will remain resident at the CRU until discharge on Day 7.

Participants will attend outpatient visits for the collection of PK blood samples and assessment of vital signs on Days 9 and 11.

Participants will be re-admitted to the CRU on Day 14 and in the morning of Day 15 will receive their second single oral dose of 160-mg selpercatinib as the capsule or tablet formulation, according to the randomization schedule, following an overnight fast of at least 10 hours. Participants will remain resident at the CRU until discharge on Day 21.

Participants will attend outpatient visits for the collection of PK blood samples and assessment of vital signs on Days 23, 25, and 28.

There will be a washout of at least 14 days between doses of selpercatinib.

6. TREATMENTS

The following is a list of the study treatment abbreviations that will be used in the TFLs.

Study Treatment Name	Abbreviation	Treatment order in TFL
160 mg selpercatinib (2 x 80 mg capsules)	Capsule	1
160 mg selpercatinib (1 x 160 mg tablet)	Tablet	2

The following is a list of the study treatment sequence abbreviations that will be used in the TFLs.

Sequence	Study Treatment Sequence Name	Abbreviation	Treatment order in TFL
1	160 mg selpercatinib (2 x 80 mg capsules) / 160 mg selpercatinib (1 x 160 mg tablet)	Capsule / Tablet	1
2	160 mg selpercatinib (1 x 160 mg tablet) / 160 mg selpercatinib (2 x 80 mg capsules)	Tablet / Capsule	2

7. SAMPLE SIZE JUSTIFICATION

The incidence of those participants with a different PK profile (2 of 19 participants in Study LOXO-RET-18015) has meant that Lilly is planning to enrol up to approximately 60 participants in Stage 1. This is to ensure that at least 50 participants will complete Stage 1 and a sufficient variation of gastric pH will be incorporated in Stage 1.

If the true intraparticipant coefficient of variation (CV) is 30% for C_{max} and 20% for the area under the concentration versus time curve (AUC), the first 50 participants in Stage 1 will give approximately 90% power to meet BE criteria at a 1-sided α level of 0.05, under an assumption of a geometric mean ratio (GMR) of 1.05.

The table below shows the required sample size for Stage 2 to provide the power for C_{max} of 90% based on different intraparticipant CV for C_{max} from Stage 1, assuming the true tablet-to-capsule GMR is 1.05 under scenario when the power is less than 90% and BE is not met at Stage 1. The actual sample size for Stage 2 will be determined based on the observed intraparticipant CV at Stage 1.

In Stage 1, dropouts will not be replaced.

In Stage 2, dropouts will not be replaced, but over-enrollment of up to 20% of the determined sample size will be permitted to ensure a sufficient number of participants.

Sample Size for Stage 2 Based on Intraparticipant CV for C_{max} in Stage 1

Intraparticipant CV for C_{max} in Stage 1	Required Sample Size for Stage 2
40%	50
50%	100
60%	156
70%	216

Note: The total sample size will be at least 50 for Stage 1 plus the required sample size for Stage 2.

8. DEFINITION OF ANALYSIS POPULATIONS

The “Safety” population will consist of all enrolled participants who received at least one dose of selpercatinib, whether or not they completed all protocol requirements, and have at least one postdose safety assessment.

The “Pharmacokinetic” population will consist of all participants who received at least one dose of selpercatinib and have evaluable PK data. Participants may be excluded from the PK summary statistics and statistical analysis if a participant has an AE of vomiting that occurs at or before 2 times median time of maximum observed drug concentration (t_{max}).

The “Pharmacodynamic” population will consist of all participants who received at least one dose of selpercatinib and have evaluable PD data. Participants may be excluded from the PD summary statistics and statistical analysis if a participant has an AE of vomiting that occurs at or before 2 times median t_{max} .

All protocol deviations that occur during the study will be considered for their severity/impact and will be taken into consideration when participants are assigned to analysis populations.

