1.2. Schema

Two by Two Crossover Design (Applicable to Stage 1 and Stage 2)

1.3. Schedule of Activities (SoA) – Stages 1 and 2

Procedure	Screening	Days																				ED
		-1	1	2	3	4	5	6	7	9	11	14	15	1 6	1 7	18	19	20	21	23	25	28
Informed consent	X																					
Inclusion and exclusion criteria	X																					
Demography	X																					
Participant Admission to CRU		X												X								
Participant Discharge from CRU									X										X			
Outpatient visit	X									X	X									X	X	X
Medical history (includes substance usage [and family history of premature cardiovascular disease]) ^a		X	X																			
Past and current medical conditions	X																					
Height and weight ^b	X	X																		X	X	

	Screening	Days																						ED
Procedure	-28 to -2 days prior to Day 1	-1	1	2	3	4	5	6	7	9	11	14	15	$\frac{1}{6}$	$\frac{1}{7}$	18	19	20	21	23	25	28		
Physical examinationc		X											X										X	X
Serum or urine pregnancy test (women of childbearing potential only)d	X	X											X										X	X
Follicle-stimulating hormone (postmenopausal women only)	X																							
Human immunodeficiency virus, hepatitis B and C screen	X																							
Urine ethanol test	X	X											X											
Urine drug screen	X	X											X											
12-lead ECGe	X	X	P, 2h	X										P, 2h		X							X	X
Vital signs (supine)f	X	X	P, 1, 2h	$\frac{2}{4}$ h						X	X	X	X	P, 1, 2h								X	X	X

	Screening	Days																								ED
Procedure	-28 to -2 days prior to Day 1	-1	1	2	3	4	5	6	7	9	11	14	15	$\frac{1}{6}$	$\frac{1}{7}$	18	19	20	21	23	25	28				
Clinical laboratory tests (include liver chemistries)g	X	X		$\frac{2}{4}$ h					X			X		$\frac{2}{4}$ h					X		X		X			
Genetic sample			X																							
Gastric pH (Stage 1 only)h			P, 0.5, 1, 1.5, 2, 2.5, 3, 3.5 h											P, 0.5, 1, 1.5, 2, 2.5, 3, 3.5 h												
PK samples - Selpercatinib (plasma)			P, 0.5, 0.75, 1, 1.5, 2, 2.5, 3, 3.5, 4, 6, 8, 12 h	2 4 , 3 6 h	48 h	72 h	96 h	12 0 h	14 4 h	X	X	X		P, 0.5, 0.75, 1, 1.5, 2, 2.5, 3, 3.5, 4, 6, 8, 12 h	2 4 , 3 6 h	4 8 h	72 h	96 h	12 0 h	14 4 h	X	X	X	X		
Randomization			X																							
Selpercatinib administration			X											X												
Adverse event /Serious adverse event review	X	X	←————→																					X		

	Screening	Days																					ED
Procedure	-28 to -2 days prior to Day 1	-1	1	2	3	4	5	6	7	9	11	14	15	¹ 6	¹ 7	18	19	20	21	23	25	28	

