2.2. Background

Selpercatinib (LY3527723) is a highly potent and specific small-molecule inhibitor of the RET kinase, with minimal inhibition of other kinase and nonkinase targets.

Selpercatinib doses have been evaluated in healthy participants or patients with advanced or metastatic RET-mutant MTC, advanced or metastatic RET fusion-positive thyroid cancer, other RET fusion-positive solid tumors, and metastatic RET fusion-positive NSCLC across Phase 1, 2, and 3 clinical studies. Across these studies, single oral doses of selpercatinib were administered over a range of 20 to 720 mg. Multiple oral doses of 160 mg/day selpercatinib were administered orally twice daily for 10 days in healthy volunteers. The most frequently reported ($\geq 15\%$ of participants regardless of attribution to study drug) Adverse events (AEs) in the ongoing first-in-human dose finding study were dry mouth, diarrhea, hypertension, AST/ALT increased, fatigue, constipation, edema peripheral, nausea, headache, blood creatinine increased, abdominal pain, rash, ECG QT prolonged, cough, vomiting, and dyspnea.

The median t_{max} of selpercatinib is 2 hours and is slowly eliminated with a mean $t_{1/2}$ of approximately 32 hours in healthy volunteers. More detailed information about the PK and absorption, distribution, metabolism, and excretion properties of selpercatinib may be found in the IB.

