9.3.3. Pharmacodynamic Analyses

The pH data will be listed and summarized using descriptive statistics.

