9.4 Pharmacodynamic Assessment

9.4.1 Pharmacodynamic Statistical Methodology

The gastric pH data (Stage 1 only) will be summarized by treatment formulation (capsule or tablet), along with changes from baseline (Day 1 or 15 predose, as applicable). A scatter plot of predose gastric pH data versus PK parameters by day will be produced, with a regression line fitted. This data will also be listed.

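### The SAP applies the PK vomiting exclusion to gastric pH at participant level, so using it drops pH readings that the vomiting cannot have affected

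*SAP*

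**What the plan says.** SAP section 8 defines a Pharmacodynamic population and attaches this rule to it: "Participants may be excluded from the PD summary statistics and statistical analysis if a participant has an AE of vomiting". The time limit comes next in the same sentence, and it covers any such event "that occurs at or before 2 times median t_{max". The PK population has the matching sentence, with PK in place of PD: "Participants may be excluded from the PK summary statistics and statistical analysis if a participant has an AE of vomiting", and the same time limit. Both sentences refer to participants. Neither mentions a dosing period, a time point or criteria for using the option.

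The pharmacodynamic data are gastric pH. Protocol 9.3.3 says only: "The pH data will be listed and summarized using descriptive statistics". SAP 9.4.1 adds summaries by formulation, changes from the predose value of each dosing day, and one display linking pH to exposure: "A scatter plot of predose gastric pH data versus PK parameters by day will be produced", with a fitted regression line.

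Protocol 1.3 (Schedule of Activities) sets the pH times on Day 1 and again on Day 15: "P, 0.5, 1, 1.5, 2, 2.5, 3, 3.5 h". A footnote there places the first reading before dosing. The two doses are separated by a washout of at least 14 days. The exploratory objective (SAP section 4) concerns initial pH. SAP section 7 gives, as one reason for the size of Stage 1, that "a sufficient variation of gastric pH will be incorporated in Stage 1".

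The population table in Protocol 9.2 has neither a pharmacodynamic population nor a vomiting exclusion, so the protocol gives no reason for the rule.

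**The concern.** Vomiting within twice the median t_max is a criterion for lost drug. It suits AUC and C_max, which depend on how much of the dose was absorbed. A pH reading depends on the state of the stomach when the sample is aspirated, so the relevant question is whether the reading came before or after the vomiting. The SAP rule does not ask that question.

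Three mismatches follow. A predose reading taken before the vomiting is removable, although predose pH is the quantity that the exploratory objective and the only pH-PK display use. A complete set of readings from the other dosing day, at least two weeks away, is removable. So are all the readings from a day on which the vomiting came after the last one.

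At stake is the completeness of the pH summaries and of the pH-PK plot, and Stage 1 was sized partly to capture variation in pH. Bioequivalence testing is not at stake, because the PD sentence does not govern it.

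**Working it through.** The plan states no figure on this point, so there is none to reproduce. The check sets the exclusion window against the pH schedule.

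**Inputs**
- pH times per dosing day: predose, 0.5, 1, 1.5, 2, 2.5, 3 and 3.5 h, which is 8 readings (Protocol 1.3).
- Dosing days: 2 (Days 1 and 15), so 8 × 2 = 16 scheduled readings per Stage 1 participant.
- Median t_max: Protocol 2.2 states that "The median t_{max} of selpercatinib is 2 hours". The median observed in this study may differ.
- Unit of exclusion: the participant (SAP section 8). Nothing in the visible text narrows it.

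**Step 1: the window.** 2 × 2 h = 4 h. It covers all 7 postdose pH times and runs 0.5 h past the last one (4 − 3.5).

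**Step 2: readings that the vomiting cannot have affected.** For one event at time *v* after dosing, let *k*(*v*) be the number of scheduled readings that day at or before *v*, with predose counted as time 0. Then

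unaffected readings = *k*(*v*) + 8,

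where the 8 are those of the other dosing day.

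| Vomiting at | *k*(*v*) | Unaffected, of 16 | Removable under SAP section 8 |
|---|---|---|---|
| 0.25 h | 1 | 9 | 16 |
| 1 h | 3 | 11 | 16 |
| 2 h | 5 | 13 | 16 |
| 3 h | 7 | 15 | 16 |
| 3.9 h | 8 | 16 | 16 |

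The range is therefore 9 to 16 of 16. At most 16 − 9 = 7 readings could have been altered.

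**Step 3: the predose case.** The rule has no lower time bound. Protocol 8.5 allows the tube to be placed up to 60 minutes before dosing, so vomiting at insertion could come before the predose reading and disturb it. Then *k* = 0 and 0 + 8 = 8 readings are unaffected. The 9-to-16 range holds for vomiting after dosing.

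**Step 4: the predose-pH versus PK plot.** Each participant contributes two points, one per dosing day, and each point needs a pH value and a PK value from the same day.
- As written, the PD rule can remove both pH values, and so both points.
- If only the PD sentence is changed, the PK rule, which is also at participant level, can still remove both PK values, and both points are still lost.
- If the vomiting-related PK exclusion is also applied by period for this plot, only the affected day's point goes and 1 of 2 stays.

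**The case against.** The strongest reply is that the sentence is permissive. Participants *may* be excluded, so an analyst who keeps the predose and other-day readings already complies with the SAP. That stands, and it rules out reading the rule as certain loss of data. It does not remove the point: no criteria govern the choice, and the only exclusion the sentence offers is of the whole participant.

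A second reply is that vomiting does bear on gastric pH, because it empties the stomach being sampled. This also stands. A reader might infer that a vomiting rule has no place in a pH analysis, but leaving out later readings on the same day is defensible, and so is leaving out a predose reading that followed vomiting at tube insertion. Only the breadth of the rule is at fault.

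Third, nothing disappears from the report. SAP 9.1 keeps excluded participants in the listings, highlighted. That is true, but listings feed neither the summaries nor the regression line.

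Fourth, a reader might try to put a number on the loss across Stage 1, or suppose that it falls on the participants with the different PK profile (2 of 19 in the earlier study cited in SAP section 7). The documents support neither. They give no vomiting rate for healthy participants and no link between vomiting and that profile. Protocol 8.5 also allows early tube removal and failed aspiration, so 16 readings is a scheduled maximum.

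**Conclusion.** The point holds as a mismatch between the rule and the data it governs. When the option in SAP section 8 is used for pH, it removes every reading a participant has, although after one postdose event 9 to 16 of the 16 scheduled readings are unaffected. On the 2 h median t_max in the protocol, an event between 3.5 h and 4 h triggers the rule when no reading on either day has been touched.

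This rests on four assumptions: a single event, vomiting after dosing, all scheduled readings obtained, and a study median t_max near 2 h. It also rests on the visible text, since part of SAP 9.3.2 is redacted.

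The impact is low. The pH work is exploratory, descriptive and confined to Stage 1. A reader might infer a threat to the bioequivalence conclusion or to the Stage 2 sample size, because Protocol 4.2 mentions pH range in connection with planning Stage 2. The documents do not support that: SAP section 10 bases the test on AUC and C_max, and the power evaluation on the C_max variability.

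**What to change.** In SAP section 8, replace the vomiting sentence for the Pharmacodynamic population with a rule by period and time point, for example:

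> If a participant vomits on a dosing day, pH readings taken after the vomiting on that day are left out of the pH summaries and changes from baseline, and are listed and flagged. Readings taken before the vomiting, and all readings from the other dosing day, are retained.

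For the plot in SAP 9.4.1, state that a point is left out for a PK reason only when the PK value from its own period is excluded. Also state that, for this plot, vomiting-related PK exclusions are applied by dosing period. Without this second part the other day's point can still be lost through the PK rule. How that rule should operate in the bioequivalence analysis is a separate question and need not be settled here.

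The cost is a few lines of SAP text and minor programming. No new data, procedures or participants are needed: the existing rule already requires the time of vomiting, and the scheduled pH times are fixed.
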